#### 2.6 Risk/Benefit Assessment

#### 2.6.1 Investigational Plan

This is a prospective multicenter Phase II clinical study employing an oral regimen administered in 3-month cycles. Patients will receive thalidomide of 50 to 100 mg once daily (QD) before bedtime, prednisone of 0.5 to 1.0 mg/kg QOD, methotrexate of 10 mg/m²/week for up to 4 cycles. Prednisone will be tapered after 3 months of dosing and dosed for up to 6 months. Patients who achieve CR can discontinue methotrexate after 4 months of consolidation therapy, with a maximum duration of 1 year. For patients who achieve PR or CR, thalidomide will be dosed for up to 2 years or discontinued at the investigator's discretion based on clinical symptoms.

Efficacy evaluation will be conducted at the end of each cycle starting from Cycle 1. The efficacy evaluations will continue until PD, discontinuation of treatment (for patients who continue treatment after PD), initiation of a new anti-cancer therapy, or withdrawal from the study (eg, death, patient's request, loss of follow-up, etc.), whichever occurs first.

The primary objective of this study is to evaluate the efficacy and safety of TPM regimen and further explore the biomarkers associated with clinical efficacy.

#### 2.6.2 Potential Risks

According to the preliminary summarized clinical safety data, the adverse reactions of thalidomide combined with immunosuppressants and hormones regimen were mainly gastrointestinal reactions and peripheral neuropathy, manifested as numbness of hands and feet, loss of appetite, constipation, dizziness, etc. However, the adverse reactions were mainly Grade 1 or 2 and could be managed. The most severe toxicities of thalidomide were embryo-fetal toxicity and venous thromboembolism. Due to the risk

of embryo-fetal toxicity and venous thrombosis. Pregnant and lactating women will be excluded from the study and those who become pregnant during the study will be promptly withdrawn from the study. Due to the risk of venous thromboembolism, high-risk patients based on the Caprini score for venous thromboembolism will be excluded from this study. Patients will take aspirin concurrently with oral thalidomide to prevent venous thromboembolism and coagulation function will be monitored at the end of each cycle. The preliminary data of this study showed that except for 1 Grade 3 nausea, no other Grade  $\geq$ 3 adverse reactions occurred and all adverse reactions were clinically manageable. The safety of thalidomide combined with methotrexate and prednisone will be monitored in this study.

#### 2.6.3 Potential Benefits

Both prospective and retrospective data indicated that the current immunosuppressive treatment had a low CRR in patients with LGLL, and the current immunotherapy has reached the "ceiling". Addressing the challenge of providing patients with more profound and durable remission remains a pressing clinical issue to be solved. LGLL is an immune disorder, immunosuppression alone is not the best choice. As an immune modulator, thalidomide combined with immunosuppressants can enhance the body's immune response to tumor cells, promote the activity of NK cells, improve the immune response of T cells, reduce the utilization of immune escape mechanisms by tumor cells, and be more targeted for the treatment of LGLL. At the same time, previous data showed that the TPM regimen had a high effective rate and CRR, far exceeding the current immunosuppressants. In addition, thalidomide combined immunosuppressants and hormones showed good safety in hematologic tumors. Therefore, it is predicted that the TPM regimen in the treatment of LGLL can further improve the effective rate and deep response rate in patients with LGLL while ensuring the safety of patients.

#### 2.6.4 Assessment of Potential Risks and Benefits

Thalidomide combined with immunosuppressants and hormones has been used in a variety of hematologic treatments. The adverse reactions are mainly gastrointestinal reactions and peripheral neuropathy, with sufficient safety information and manageable risks. Previous data showed that TPM regimen had a good effective rate and CRR in patients with LGLL. In this study, the adverse reactions of patients during treatment will be closely monitored and treated in a timely manner until they return to normal or reach clinical stability.

Therefore, the risk of this study is manageable, and the expected benefits outweigh the risks.

## 3. Objectives

#### **Primary Objective:**

• To evaluate the CRR of symptomatic LGLL patients treated with TPM regimen

## **Secondary Objectives:**

- To evaluate the safety and tolerance of symptomatic LGLL patients treated with TPM regimen
- To evaluate the ORR and PR rate of symptomatic LGLL patients treated with TPM regimen
- To evaluate the PFS and OS of symptomatic LGLL patients treated with TPM regimen
- To evaluate the duration of response (DoR) in symptomatic LGLL patients treated with TPM regimen

### **Exploratory Objective:**

• To explore biomarkers significantly and potentially associated with clinical efficacy

[figure not shown]
## 4. Study Design

## 4.1 Overall Study Design

This is a prospective multicenter Phase II clinical study employing an oral regimen administered in 3-month cycles. Patients will receive thalidomide of 50 to 100 mg QD before bedtime, prednisone of 0.5 to 1.0 mg/kg QOD, methotrexate of 10 mg/m²/week for up to 4 cycles. Prednisone will be tapered after 3 months. Patients who achieve CR can discontinue methotrexate after 4 months of consolidation therapy, with a maximum duration of 1 year. For patients who achieved a partial remission (PR) or CR, Thal maintenance therapy was recommended to be continued for a maximum duration of two years, but also depended on patients or investigator's choices.

Efficacy evaluation will be conducted at the end of each cycle starting from Cycle 1. The efficacy evaluations will continue until PD, discontinuation of treatment (for patients who continue treatment after PD), initiation of a new anti-cancer therapy, or withdrawal from the study (eg, death, patient's request, loss of follow-up, etc.), whichever occurs first.

The primary objective of this study is to evaluate the efficacy and safety of TPM regimen and further explore the biomarkers associated with clinical efficacy.

Abbreviations: CR, complete remission; MTX, methotrexate; Pred, Prednisone; Thal, thalidomide.

Notes:

Thal: 50 to 100 mg, oral, before bed, for 2 years;

Pred: 0.5-1 mg/kg, oral, every other day, could be tapered after 3 months of dosing and dosed for up to 6 months

MTX: 10 mg/m^2, once weekly, patients who achieve CR can discontinue MTX after 4 months of consolidation therapy, with a maximum duration of 1 year.

## 4.2 Description of Overall Study Design and Plan

The study consists of a 28-day screening period, a treatment period (up to half a year for prednisone, up to 1 year for methotrexate, and 2 years for thalidomide), and a follow-up period (safety and efficacy follow-up). Patients who provide the signed

informed consent will undergo baseline examinations during the screening period. Prior treatment and efficacy will also be evaluated before enrollment. Patients who met the inclusion/exclusion criteria will enter the treatment period. Relevant examinations specified in the protocol will be completed for all patients during treatment to observe efficacy, safety, and hemogram changes after discontinuation of the study drugs. The follow-up period will begin after the end of the treatment period.

#### 4.3 Duration of Treatment

Patients enrolled in this study will be treated with thalidomide combined with methotrexate and prednisone for 3 months and then evaluated for efficacy. Based on the efficacy evaluation, patients will either continue treatment as per the initial regimen or be withdrawn from the study. The Institute of Hematology and Blood Diseases Hospital, Chinese Academy of Medical Sciences, is a specialized hospital for hematology, where treats 30 to 40 LGLL patients every year, of which approximately 5 to 10 are eligible for enrollment. A total of 5 to 10 patients are expected to be enrolled in multiple centers nationwide every year. The enrollment period of this study is expected to span 2 years. This study is of a limited course of treatment. Patients who obtain sustained clinical benefits from the study treatment without consent withdrawal, PD, and intolerable toxicity may continue the study and receive follow-up. The end of study (EOS; study completion) is defined as the time when the last patient completes the last visit.

## 4.4 Follow-up

Patients who withdraw from the study due to intolerable AEs will be followed up in this study until the events resolve to Grade 1 or lower, or the AE is stable. Patients will be followed up for up to 24 months after completion of the treatment, or until study termination, PD, initiation of new anti-tumor therapy, or death.

## 4.5 Sample Size

A retrospective study of 45 patients is used as the historical control, in which cyclophosphamide monotherapy was applied with an effective rate of 72% and CRR of 47%. From the perspective of clinical expertise, taking the CRR of 70% as the minimum threshold for clinical significance, the sample size of 35 patients in this group is deemed sufficient to test the overall true CRR that is superior to that of the historical control at a false positive rate  $\alpha = 0.05$  (two sides) and false negative rate  $\beta = 0.2$  (ie, power = 80%). With a 20% dropout rate, at least 42 patients would be required to enroll in this study.

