#### **Sample Size:**

A retrospective study of 45 patients is used as the historical control, in which cyclophosphamide monotherapy was applied with an effective rate of 72% and CRR of 47%. From the perspective of clinical expertise, taking the CRR of 70% to 80% as the minimum threshold for clinical significance, the sample size of 35 patients in this group is deemed sufficient to test the overall true CRR that is superior to that of the historical control at a false positive rate  $\alpha = 0.05$  (two sides) and false negative rate  $\beta = 0.2$  (ie, power = 80%). With a 20% dropout rate, at least 42 patients would be required to enroll in this study.

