#### **Efficacy Analysis:**

The efficacy analysis will involve CRR and ORR (sum of CR and PR rates). Efficacy variables will be tabulated and summarized. For the numbers and percentages of CRR and ORR, point estimates and 95% exact binomial CIs will be provided.

Time-to-event variables including DoR, PFS, and OS will be summarized descriptively using the Kaplan-Meier method. The rules for DoR, PFS, and OS, analyses will be specified in the Statistical Analysis Plan (SAP). Growth modulation indices (intrasubject ratios of DOR, PFS, and OS, post-study treatment versus DOR, PFS, and OS post the most recent prior treatment regimen) will be summarized.

Data will be summarized using descriptive statistics. Continuous variables will be presented as number, mean, standard deviation, median, and range. Discrete variables will be summarized as frequency.

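### With 35 evaluable patients the attained power against a CRR of 47% is 77.3% at a true CRR of 70%, slightly below the 80% stated in Section 4.5

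*Supplement*

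**What the plan says.** Section 4.5 takes a retrospective series of 45 patients as historical control, in which "cyclophosphamide monotherapy was applied with an effective rate of 72% and CRR of 47" percent was seen. It sets the target by "taking the CRR of 70% as the minimum threshold for clinical significance" and states that "the sample size of 35 patients in this group is deemed sufficient to test the overall true CRR" superior to the control, at a two-sided alpha of 0.05 and a power of 80%. Enrolment is then raised: "With a 20% dropout rate, at least 42 patients would be required to enroll in this study".

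The synopsis repeats this paragraph with one difference, "taking the CRR of 70% to 80% as the minimum threshold for clinical significance".

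Neither place names the test or the number of remissions that would count as success. For the CRR, Section 11.3 and the synopsis say only that "point estimates and 95% exact binomial CIs will be provided". The tests listed in Section 11.1 (chi-square, Cochran-Mantel-Haenszel, log-rank) compare groups, and this trial has one arm. The supplement shows no separate SAP.

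**The concern.** A stated power is a claim about the chance of success under a definite rule. Here the sample size matches a large-sample formula, while the interval planned for the primary endpoint is exact. With 35 patients each remission moves the observed rate by 1/35, or 2.9 points, so the rule that can actually be applied may be stricter than the smooth formula assumes.

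Two things are at stake. The stated risk of missing a regimen that truly reaches 70% is 20%, and the attained risk may be higher. And a reader of Section 4.5 cannot see where the line falls between a result that supports superiority to 47% and one that does not.

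**Working it through.** **Inputs.** Null rate p0 = 0.47, target p1 = 0.70, two-sided alpha 0.05, power 0.80 and n = 35, all from Section 4.5. The table in Section 2.2 gives the control as 21/45 = 46.7%. The exact interval is from Section 11.3.

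**1. Reproducing 35.** One-sample normal approximation:

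n = [z(0.975)·√(p0(1−p0)) + z(0.80)·√(p1(1−p1))]² / (p1−p0)²

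= [1.960·√(0.47·0.53) + 0.842·√(0.70·0.30)]² / 0.23² = 35.16

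The arcsine version gives 35.3. Approximate power at n = 35 is Φ[(0.23·√35 − 1.960·√0.2491)/√0.21] = Φ(0.835) = 79.8%. The stated 35 and 80% are therefore reproduced to within rounding.

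**2. Critical count at n = 35.**

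| Remissions | Observed CRR | Lower exact 95% limit | P(X ≥ r) at 47% | Score z |
|---|---|---|---|---|
| 22/35 | 62.9% | 44.9% | 0.0435 | 1.88 |
| 23/35 | 65.7% | 47.8% | 0.0200 | 2.22 |

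Score z = (r/35 − 0.47)/√(0.47·0.53/35), with denominator 0.0844. A two-sided 5% test needs an upper tail of at most 0.025, or z of at least 1.96. The exact interval and the score test therefore both first exclude 47% at 23/35. A Wald test also fails at 22/35 (z = 1.94) and needs 23.

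With the unrounded 21/45 as the null the cut-off does not move: the lower limit at 22/35, 44.9%, is still below 46.7%, and the upper tails are 0.040 at 22 and 0.018 at 23.

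**3. Attained power.** P(X ≥ 23 | n = 35, p = 0.70) = 0.773. The risk of missing a true 70% is 1 − 0.773 = 22.7%, and the gap to the stated power is 80.0 − 77.3 = 2.7 points.

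**4. Dependence on the number analysed** (exact rule, true CRR 70%).

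| n | Needed | Power |
|---|---|---|
| 35 | 23 | 77.3% |
| 36 | 24 | 73.7% |
| 37 | 24 | 80.7% |
| 38 | 25 | 77.4% |
| 39 | 25 | 83.6% |
| 40 | 26 | 80.7% |
| 41 | 27 | 77.6% |
| 42 | 27 | 83.6% |

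Power is above 80% at every size computed from 42 to 69. The exact and score rules coincide at 35 but not everywhere: at 36 the score test needs 23 (power 83.7%), so the named test matters as soon as n departs from 35.

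**5. Dependence on the target, n = 35 and at least 23 remissions.** Power is 77.3% at 70%, 81.1% at 71% and 98.6% at 80%.

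**The case against.** Most of the other side's case concerns weight, and much of it stands.

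- **A reader might infer that 35 is a calculation error, rounded down from 35.16.** The documents do not support that. Section 4.5 names no formula, and with 21/45 as the null the same formula gives 34.1, which rounds up to 35.
- **A reader might infer that the trial breaks its own success criterion.** It has no such criterion in the text shown. Section 11.3 offers the exact interval beside a point estimate, and an SAP not shown here may hold the decision rule. Treating the interval as the test is an inference, but the 77.3% does not hang on it, since the two-sided score and Wald tests need the same 23. A one-sided 5% rule would accept 22/35 with 86.5% power, but Section 4.5 specifies two sides.
- **A reader might infer that the trial is seriously underpowered or needs more patients.** The gap is 2.7 points and comes from discreteness; the attained upper-tail error is correspondingly conservative (0.020 against 0.025). The 70% is a clinical judgement, and one more point in it brings power above 80%. If all 42 enrolled patients were evaluable, exact power would be 83.6%.

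That last argument does not rescue the stated figure. Section 4.5 attaches 80% to 35 patients and adds the rest to cover dropout, and Section 9.1.1 limits which patients count as evaluable for response.

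**Conclusion.** The point holds as a small mismatch between the sizing approximation and the power the design attains: 77.3% instead of 80%, a miss risk of 22.7% instead of 20%. It rests on 47% being treated as a fixed null, a true CRR of exactly 70%, a two-sided 5% level and exactly 35 evaluable patients. It is the same for the exact interval, the score test and the Wald test, and for 47% or 21/45 as the null.

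It does not call the design into question. Its practical value lies mainly in making the dividing line visible: 22/35 (63%) does not exclude 47%, and 23/35 (66%) does.

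Nor should 77% simply be written into the synopsis as it stands. Its target runs from 70% to 80%, over which exact power at 35 runs from 77.3% to 98.6%, so no single power belongs to it until the two statements of the target agree.

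**What to change.** - In Section 4.5, give the power as about 77% for 35 evaluable patients at a true CRR of 70%, by the exact binomial method.
- State the success rule there: lower exact 95% limit above 47%, which means at least 23 of 35 remissions. Add that the critical count will be recomputed for the number actually analysed, for example at least 27 of 42 (power 83.6%).
- In the synopsis, first bring the 70% to 80% target into line with the 70% of Section 4.5, then give the same power and rule.

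The cost is wording in two places and a slightly less favourable stated power. No extra patients are needed.

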# 11.3 Efficacy Analysis

The efficacy analysis will involve CRR and ORR (sum of CR and PR rates). Efficacy variables will be tabulated and summarized. For the numbers and percentages of CRR

and ORR, point estimates and 95% exact binomial CIs will be provided.

Time-to-event variables including DoR, PFS, and OS will be summarized descriptively using the Kaplan-Meier method. The rules for DoR, PFS, and OS analyses will be specified in the Statistical Analysis Plan (SAP). Growth modulation indices (intrasubject ratios of DOR, PFS, and OS, post-study treatment versus DOR, PFS, and OS post the most recent prior treatment regimen) will be summarized.

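### The 20% dropout allowance is miscalculated (42 enrolled instead of 44), the synopsis and Section 4.5 give different target CRRs, and no test is named for the stated 80% power

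*Supplement*

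**What the plan says.** Section 4.5 of protocol version 2.0 takes its reference from a retrospective series of 45 patients in which "cyclophosphamide monotherapy was applied with an effective rate of 72% and CRR of 47"%. It sets the target by "taking the CRR of 70% as the minimum threshold for clinical significance" and concludes that "the sample size of 35 patients in this group is deemed sufficient to test the overall true CRR" is superior to the historical rate, with two-sided α = 0.05 and 80% power. The dropout step follows: "With a 20% dropout rate, at least 42 patients would be required to enroll in this study".

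The synopsis (Sample Size) repeats the 35 and the 42 but words the target differently: "taking the CRR of 70% to 80% as the minimum threshold for clinical significance".

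Neither place names the test or formula behind the 35. Section 11.3 says that for CRR and ORR "point estimates and 95% exact binomial CIs will be provided", without stating a comparison with 47%. Section 11.1 mentions a χ² test for an overall comparison and describes comparisons between two treatment groups, which a single-arm trial does not have. Section 9.1.1 restricts evaluable responses to patients with measurable disease at baseline, at least one cycle of treatment and a re-evaluation; progression or death by the end of Cycle 1 also counts as evaluable. No primary analysis set is named.

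**The concern.** This paragraph is the only justification for the size of the trial. A dropout allowance should leave the required number of evaluable patients after the losses, and 42 with 20% loss does not leave 35. A reader can see this with one multiplication.

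Two further points bear on the same paragraph. The synopsis and Section 4.5 give different target rates for the primary endpoint while arriving at the same 35. And the 80% power is tied to no named test, although the only method Section 11.3 specifies for CRR is an exact interval, under which 35 patients give somewhat less than 80%. At stake is whether the stated size and power describe the design that will be run and analysed.

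**Working it through.** **Inputs.** From Section 4.5: p0 = 0.47 (treated as a known constant), p1 = 0.70, two-sided α = 0.05 (0.025 in the upper tail), power 0.80, n = 35, dropout 20%, enrolled 42. From the synopsis: p1 = 0.70 to 0.80.

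**1. Reproducing the 35.** One-sample normal approximation:

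n = [(1.96·√(p0(1−p0)) + 0.8416·√(p1(1−p1))) / (p1−p0)]²

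- p1 = 0.70: [(1.96·√0.2491 + 0.8416·√0.21)/0.23]² = [(0.978 + 0.386)/0.23]² = 35.2
- p1 = 0.80: [(0.978 + 0.8416·√0.16)/0.33]² = [(0.978 + 0.337)/0.33]² = 15.9

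So the 35 follows from 70% and not from 80%. Power at a given n on the same approximation is Φ[(√n·0.23 − 0.978)/√0.21]. At n = 35 this is Φ(0.835) = 79.8%, so the stated 80% reproduces to rounding.

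**2. The dropout step.**

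- 35 × 1.2 = 42, which is the stated figure
- 42 × 0.8 = 33.6 evaluable, short of 35
- 35/0.8 = 43.75, so 44 enrolled
- 1 − 35/42 = 16.7%, the dropout that 42 really covers

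**3. Cost of the slip on the approximation that gives 35.** Power is 78.6% with 34 evaluable and 77.3% with 33, against 79.8% with 35: a loss of about 1 to 3 points.

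**4. Power if the exact interval decides.** Suppose success means that the lower limit of the exact 95% CI lies above 47%. This is the same as an exact binomial test with upper-tail α ≤ 0.025.

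| Evaluable n | CRs needed | Upper-tail α at 47% | Power at 70% |
|---|---|---|---|
| 33 | 22 | 0.018 | 73.3% |
| 34 | 23 | 0.012 | 69.3% |
| 35 | 23 | 0.020 | 77.3% |

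The drop at n = 34 arises because the cut-off moves from 22 to 23. If each of 42 enrolled patients independently has a 20% chance of dropping out, so that the evaluable number is Bin(42, 0.8), average power under this rule is 72%.

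**5. If all 42 treated patients are analysed.** With dropouts counted as non-CR, the exact rule is at least 27 of 42 CRs: one-sided α 0.018 and power 83.6%, provided that the CRR among all treated patients is 70%. If 70% applied only to those who stay and 20% drop out as failures, the all-treated rate would be 0.8 × 70% = 56%, and the 83.6% would not apply.

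**The case against.** The strongest reply is that the power statement is not an error. The inputs in Section 4.5 put into the standard one-sample formula give 35.2 patients and 79.8% power. Section 11.3 offers exact intervals as summary reporting and names no test of CRR against 47%. A reader might infer that the plan promises 80% power and fails to reach it, or that the dropout slip brings power down to 69%. The documents support neither reading:

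- The 77.3% is the gap between an exact and an approximate method.
- The 69.3% at n = 34 is a discreteness effect. It lies below the value at n = 33, and another valid exact two-sided test, which orders outcomes by likelihood, gives 80.7% at n = 34.
- Enrolling 44 would leave about 35 evaluable patients, where exact power is still 77.3%. Most of the distance from 80% is therefore not caused by the dropout step.

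It can also be said that 42 is stated as a minimum, that the shortfall is two patients, and that dropouts may not leave the denominator at all, since Section 9.1.1 keeps early progressions and deaths and no primary set is named. On the target, the lower end of a 70% to 80% range governs sizing, and at a true CRR of 80% exact power with 35 patients is 98.6%.

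All of this stands, and it keeps the point small. Three things remain: 42 does not cover 20% dropout, two current passages disagree on the target, and the power cannot be attached to a stated test or analysis set. That significance at 23/35 (66%) falls below the 70% called a minimum threshold is a matter of labelling, since 70% serves here as the planning alternative.

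**Conclusion.** The concern holds in a limited form and is minor. The enrolment figure is wrong by two patients for the dropout rate the plan assumes: 44 are needed, and 42 covers 16.7%. On the normal approximation that reproduces the 35, this costs about 1 to 3 points of power. If the exact interval is the decision rule, power is 77.3% with 35 evaluable and about 72% averaged over 20% dropout from 42. The synopsis range conflicts with Section 4.5, and only 70% gives 35.

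The exact figures assume that success means an exact 95% lower limit above 47%, that dropouts leave the denominator, and that dropout is independent between patients. All figures treat 47% as known, although it comes from 45 patients. The documents do not support a claim that the 80% was miscalculated; they leave open which test it belongs to.

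**What to change.** In Section 4.5 and the synopsis:

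1. State that 42 enrolled covers 16.7% dropout with 35 evaluable, and that 20% would need 44.
2. Use 70% as the single target in both places and call it the planning alternative.
3. Name the primary test of CRR against 47% and the primary analysis set, and carry the same rule into Section 11.3.
4. Report the power of that test: 79.8% by the normal approximation or 77.3% by the exact method (at least 23 CRs) with 35 evaluable. If all 42 treated patients are analysed with dropouts as non-CR, give the rule as at least 27/42 CRs, with one-sided α 0.018 and power 83.6%, and state that this assumes a 70% CRR among all treated.

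This changes wording only and adds no patients if 42 is kept; providing for the full 20% adds two. The downside is a slightly less favourable stated dropout allowance or power.

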# 9. Efficacy Evaluation

## 9.1 Definition

### 9.1.1 General Definition

Evaluable toxicity: All patients who have received at least 1 month of TPM treatment are evaluable for toxicity evaluation from the first treatment.

Evaluable objective response: Only patients who have a measurable disease at baseline, have received at least 1 treatment cycle, and have been re-evaluated for the disease will be considered as evaluable responses. These patients will be categorized for their responses according to the following definitions (Note: Patients who demonstrate objective PD or death by the end of Cycle 1 will also be considered evaluable).

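### The enrolment target of 42 does not cover 20% dropout from the 35 patients needed: it covers 16.7%, and 20% would need 44 (a minor correction)

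*Supplement*

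**What the plan says.** Section 4.5 builds the sample size on a historical control in which "cyclophosphamide monotherapy was applied with an effective rate of 72% and CRR of 47" per cent. The target is set by "taking the CRR of 70% as the minimum threshold for clinical significance". With a two-sided alpha of 0.05 and 80% power, "the sample size of 35 patients in this group is deemed sufficient". The paragraph closes with the enrolment figure: "With a 20% dropout rate, at least 42 patients would be required to enroll in this study".

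The sample-size paragraph of the synopsis gives the same 35, 20% and 42, though it words the target CRR as a range of 70% to 80%. Neither place gives the formula that leads from 35 to 42.

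Section 9.1.1 says who counts for response: patients with measurable disease at baseline who "have received at least 1 treatment cycle, and have been re-evaluated for the disease will be considered as evaluable responses". Patients with progression or death by the end of Cycle 1 also count. The protocol does not say that dropouts are replaced, or that they are kept in the CRR denominator as non-responders.

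**The concern.** A dropout allowance should leave the required number of patients after the stated loss. Here the required number is 35 and the stated loss is 20%, but a 20% loss from 42 leaves fewer than 35. The enrolment target, the dropout rate and the evaluable number behind the power statement cannot all be true.

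Section 9.1.1 makes this more than a matter of wording. A patient who leaves before completing a cycle and being re-evaluated, without progression or death by then, drops out of the response denominator. That is the loss an allowance is meant to cover. The stated power for the primary endpoint depends on the 35, and 35 has no slack, as the working shows.

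**Working it through.** **Inputs**, from section 4.5 unless noted: null CRR p0 = 0.47; target CRR p1 = 0.70 (the lower end of the synopsis range); alpha 0.05 two-sided, z = 1.960; power 0.80, z = 0.842; 35 patients in one group; dropout 20%; enrolment 42.

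**Step 1: reproduce the 35.** One-sample proportion against a fixed rate, normal approximation:

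n = [z(0.975)·√(p0(1−p0)) + z(0.80)·√(p1(1−p1))]² / (p1−p0)²

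= [1.960 × 0.4991 + 0.842 × 0.4583]² / 0.23²

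= [0.9782 + 0.3857]² / 0.0529 = 35.2

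The arcsine version gives 35.3. The 35 is reproduced to within rounding, with nothing to spare. The protocol does not name its method, so this approximation is inferred from the match.

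**Step 2: the dropout allowance.**

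- Needed for 20% loss: 35/(1 − 0.20) = 43.75, so 44. Check: 44 × 0.80 = 35.2.
- Left from 42 after 20% loss: 42 × 0.80 = 33.6, so 33 or 34.
- Loss that 42 does cover: (42 − 35)/42 = 7/42 = 16.7%.
- 35 × 1.20 = 42 exactly. This suggests that 20% was added to 35, where 35 should have been divided by 0.80.

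**Step 3: what it costs in power.** Same normal approximation:

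power = Φ{[(p1−p0)√n − 1.960·√(p0(1−p0))] / √(p1(1−p1))}

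For n = 35: (0.23 × 5.916 − 0.9782)/0.4583 = 0.835, so 79.8%.

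For comparison, exact binomial power takes the smallest number of CRs whose upper-tail probability under 47% is at most 0.025.

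| Evaluable | Normal approximation | Exact binomial (CRs needed) |
|---|---|---|
| 35 | 79.8% | 77.3% (23) |
| 34 | 78.6% | 69.3% (23) |
| 33 | 77.3% | 73.3% (22) |

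By the method that gives 35, the loss is 79.8 − 78.6 = 1.2 points at 34 and 79.8 − 77.3 = 2.5 points at 33. The exact column moves up and down because the cut-off is a whole number: power is lower at 34 than at 33, and it falls again to 73.7% at 36.

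**The case against.** The arithmetic is hard to dispute. The wording "at least" does not rescue it, because 42 is offered as the minimum that covers 20%, and it does not. The case on the other side concerns size, and most of it stands.

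- **The gap is two enrolled patients.** No analysis or conclusion turns on it.
- **A reader might infer that power falls from 80% to about 70%.** The exact figures of 69.3% and 73.3% invite this, but the comparison mixes methods. The stated 80% matches the normal approximation. By the exact method even 35 evaluable patients give 77.3%, so 2.7 points of the apparent fall have nothing to do with dropout. Part of the rest is discreteness. Nor do the documents make the exact calculation the decision rule: section 11.3 gives exact binomial intervals beside the point estimates, and section 11.1 names a chi-squared test for an overall comparison. Neither sets out a one-sample test of the primary endpoint against 47%.
- **A reader might infer that 33 to 34 evaluable patients is certain at 20% dropout.** The protocol does not define dropout. Under section 9.1.1 a patient who leaves after one cycle and a re-evaluation still counts, as does one with progression or death by the end of Cycle 1. Thalidomide treatment runs up to 2 years. If the 20% refers to the whole study, many dropouts would remain in the CRR analysis, and 33 to 34 is then the low end.
- **The origin of 42 is not documented.** Multiplying 35 by 1.20 fits exactly, but no formula is stated. The mismatch does not depend on this explanation.

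Keeping dropouts in the denominator as non-responders would not restore the stated figures either. If, as an assumption, all 20% counted as not in CR, the expected CRR would be 0.70 × 0.80 = 56%, well below the 70% used for the 35.

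**Conclusion.** The stated figures are wrong as written, in section 4.5 and in the synopsis: 42 enrolled patients do not leave 35 after 20% dropout. They leave 33.6. The number matching 20% is 44, and 42 matches 16.7%.

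The effect on power is about 1 to 2.5 percentage points (from 79.8% to between 77.3% and 78.6%). This assumes a null of 47%, a true CRR of 70%, two-sided 0.05, the normal approximation that reproduces 35, and every dropout being lost to the CRR analysis. If some dropouts stay evaluable, the effect is smaller.

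The point is a minor correction of a stated figure. It does not show that the design is inadequate, and the exact-binomial values should not be read as the size of this error.

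**What to change.** Change the closing sentence of the sample-size paragraph in section 4.5, and the same sentence in the synopsis, in one of two ways:

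1. Keep 42 and state that it allows for about 16.7% dropout (7 of 42 patients).
2. Keep 20% and give 44 as the number to enrol (35/0.80, rounded up).

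If 42 and 20% are both to stay, add that 33 to 34 evaluable patients are then expected and that power is about 77 to 79% by the same normal approximation. An exact-binomial figure should not be set beside the 80% unless the 80% is recalculated in the same way.

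The cost is one sentence in two places. The first option and the fallback need no extra patients; the second needs two more. It would help to say in the same sentence what counts as a dropout for the CRR analysis.
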